Although TENS is effective for several pain conditions such as osteoarthritis, chronic musculoskeletal pain, and postoperative pain [6;22;41], its effectiveness in treatment of people with fibromyalgia is virtually unknown. Furthermore, there is a general thought among clinicians that since fibromyalgia pain is widespread, TENS would be ineffective in this population. To initially test if TENS was effective in decreasing the pain associated with fibromyalgia we performed a preliminary study examining the effectiveness of a single treatment with high frequency TENS. The group receiving active TENS showed a reduction in resting pain and pain during movement compared with placebo. There were also improvements in measures of function in the active TENS group with a greater increase in distance walked in the 6 minute walk test (by 221 feet) as compared to a decrease in distance (-100 feet) for placebo. TENS also increased pressure pain thresholds (by 20%) during DNIC when compared to virtually no change for placebo TENS (1%). Thus, TENS may decrease pain associated with fibromyalgia by increasing central inhibition and decreasing central excitability. This decrease in pain is expected to increase function and improve quality of life.

[figure not shown]

Figure 1: Conceptual Model for TENS effects

Hypothesis

We hypothesize that application of Transcutaneous Electrical Nerve Stimulation (TENS) to patients with fibromyalgia will reduce resting and movement-related pain and reduce central excitability by restoring diffuse noxious inhibitory controls (DNIC), and that this decrease in pain and/or central excitability will reduce fatigue and fear of movement, thereby improving function and quality of life (see Figure 1).

Aims

Aim #1: The primary aim of the study is to test the effectiveness of repeated TENS use on movement-related pain in people with fibromyalgia with random assignment to three treatments: standard care, placebo TENS and active

Aim #2: A secondary aim will test if pain reduction by TENS results in a concomitant decrease in fatigue and fear of movement, and an increase in function and quality of life. Outcome measures will include physical function by directly assessing daily activity with an accelerometer, as well as performing specific functional tasks

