
Statistical Methods Aim #1- #4
	
Aim #1: The primary endpoint of Aim #1 is the change (visit 3- visit 2) in pain scores during movement. In order to evaluate the effectiveness of long-term use of TENS (Aim 1), the primary analysis will be the comparison of change in pain (with movement for those randomized to either active TENS, placebo TENS, or standard of care). The comparison of the change (visit 3 – visit 2) in pain for the three groups will be made using linear mixed model analysis for repeated measures with treatment group, time (visit2 and visit3), and treatment group*time interaction as the fixed effects. The test for the treatment group*time interaction effect corresponds to the test comparing mean change among the groups. Post-hoc pairwise comparison of mean change between groups will performed by test of mean contrasts estimated from the fitted linear mixed model with p-values adjusted using Bonferonni’s method to account for the number of tests performed (i.e. 3 tests for all pairwise comparisons). It is expected that the randomization will lessen the need for covariate-adjusted analyses. However, in the event that adjusted analyses are necessary, a secondary comparison of the change in endpoints for the three groups will be made by expanding the linear mixed model to include covariates. Potential confounders include age, race, ethnicity, educational attainment, marital status, TENS dose/intensity, change in opioid status, medication intake and use of rescue medications.
 
While every effort will be made to follow-up with patients, preliminary data suggests that approximately 10% of the patients will not return for follow-up. The ITT analysis will be performed using all available data for all randomized participants. In the presence of missing data, under the assumption of missing at random (MAR), linear mixed model analysis which can handle incompletely observed subjects and uses a likelihood estimation method will provide correct likelihoods and lead to valid estimates (ref1). However, since the data under analysis cannot distinguish if data is MAR or it is missing not at random (MNAR), sensitivity analysis will also be performed using pattern mixture models. Multiple imputations will be used for sensitivity analysis by imputing from a non-random pattern mixture model (ref2).
 
Furthermore, based on previous work, it is expected that approximately 5% of subjects randomized to active TENS may not receive a full dose of active TENS because they did not achieve the adequate intensity dose. In the primary ITT analysis, these patients will be included as randomized. However, as an additional analysis a modified ITT (mITT) analysis will be conducted. This analysis will utilize an ITT principle in terms of randomization but will be limited to those who achieved at least one adequate intensity dose.
 
(ref1) Molenberghs G. and Kenward MG (2007) Missing Data in Clinical Studies. John Wiley & Sons Ltd, West Sussex, England.

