
(ref2) Carpenter J and Kenward MG (2013) Multiple Imputation and its Application. John Wiley & Sons Ltd, West Sussex, England.

Aim #2: The primary endpoint of Aim #2 is the change (visit 3 – visit 1) in fear of movement scores. Secondary endpoints for this aim include changes in function, fatigue, resting pain, function, use of rescue analgesic medications, and quality of life. Additionally physical function measures will be determined using accelerometer data and data obtained during a course of specific functional tasks. Rescue analgesic medications will be recorded as number and dose of medications, indicators for increases or decreases in frequency or dose, and any utilization. Comparisons between the randomized groups for these outcomes will be performed as described in Aim 1. Additional analyses, using the change in fatigue, fear of movement, function, quality of life and resting pain measures as dependent variables in linear regression models, associations between these outcomes and changes in pain values will be investigated.

Aim #3: The primary endpoints of Aim #3 are the change (visit 3 – visit 2) in PPT and DNIC/CPM for those who complete one month of active TENS. After one month of active TENS, participants will be clinically evaluated and classified as responders or non-responders using recently published criteria for fibromyalgia subjects [7]. Comparisons of these physiologic parameters will be made in responders versus non-responders as described in Aim 1. Since responder status is not randomized, it is expected that that the linear mixed model will also include covariates such as change in opioid status, medication intake, and TENS use. Multiple variable logistic regression (with associated odds ratio estimates and ROC curves) will also be utilized to investigate factors related to being a responder or not.

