Aim #1	V3-V2	Pain NRS with movement (6MWT and FTSTS) for the treatment groups: active TENS, placebo TENS or standard care	
 • Linear mixed model analysis (LMM) for repeated measures with treatment group, time (V3-V2) and treatment group*time interaction as fixed effects. • Post-hoc pair wise comparison of mean change between all three treatment groups • p-values adjusted using Bonferroni method to account for the number of tests • Potential confounders include BMI, age, race, ethnicity, educational attainment, marital status, TENS dose/intensity, change in opioid status, medication intake, rescue medications; If there are differences between potential confounders, we will include covariates
Aim #1 Intention to Treat (ITT)	V3-V2	Pain NRS with movement (6MWT and FTSTS) for the treatment groups: active TENS, placebo TENS or standard care	
 • Intention to treat (ITT) analyses using all available data for all randomized participants will be used • If there are missing data, missing at random (MAR) LMM will be used. Sensitivity analysis will be performed using pattern mixture models since data cannot be determined if it is MAR or missing not at random (MNAR). Multiple imputation will be used for sensitivity analysis by imputing from a non-random pattern mixture model • Modified ITT (mITT) will be conducted to account for subjects who did not achieve adequate dose (based on previous work, 5% of subjects randomized to active TENS

			are expected to not achieve adequate dose). This will be limited to those who achieved at least one adequate intensity dose ^{73, 74} .
Aim #2	V3-V2	Primary: Fear of movement scores. Secondary: changes in function, fatigue, resting pain, use of rescue medications, accelerometry and quality of life questionnaires.	
 • Comparison between the randomized groups will be performed as described in Aim #1. • Additional analysis using the change in fatigue, fear of movement, function, resting pain measures and quality of life as dependent variable in linear regression models, associations between these outcomes and changes in pain values will be investigated.

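### Aim #2's additional regressions name change in pain as the only predictor; without randomised arm and baseline values they can report a pain–fear link that is only a difference between arms

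*Combined protocol and SAP*

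**What the plan says.** The Aims section sets Aim #2 as a question about a pathway: to "test if pain reduction by TENS results in a concomitant decrease in fatigue and fear of movement", with gains in function and quality of life. The Hypothesis states the same chain, that "this decrease in pain and/or central excitability will reduce fatigue and fear of movement, thereby improving function and quality of life".

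The Study Synopsis (Statistical Methods, Aim #2) then gives two kinds of analysis.

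- **Randomised comparison.** "Comparisons between the randomized groups for these outcomes will be performed as described in Aim 1". The Aim #1 model is a linear mixed model with "treatment group, time (visit2 and visit3), and treatment group*time interaction as the fixed effects". It has treatment terms and no pain term.
- **Regressions.** "Additional analyses, using the change in fatigue, fear of movement, function, quality of life and resting pain measures as dependent variables in linear regression models", in which "associations between these outcomes and changes in pain values will be investigated".

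The Aim #2 row of the Data Analysis Plan table repeats both, again without a treatment term, covariates or an analysis set for the regressions. No indirect-effect (mediation) analysis is planned anywhere.

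The two places disagree on the window for change in fear of movement. The Synopsis uses visit 3 minus visit 1, and the table uses V3-V2. Tables 1 and 3 schedule the TSK only at visits 2, 3 and 4.

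**The concern.** The randomised comparison can show that TENS changes fear of movement. It cannot show that pain relief is what changed it. That part of Aim #2 rests on the regressions alone.

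If the regressions are run across the randomised arms with change in pain as the sole predictor, the slope has two sources: patients within an arm whose pain and fear move together, and arms that differ in their average change on both. The second source gives a positive slope even when no patient's fear follows her pain. The plan's own hypothesis allows a route other than pain, through central excitability. One arm also receives no device, so expectation may differ between arms and move both self-reports.

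Elsewhere the plan names adjustment where it intends it. Aim #1 lists potential confounders, Aim #3 expects covariates because responder status is not randomised, and Aim #4 may control for confounders. Change in pain is not randomised either, but the Aim #2 regressions carry no such provision. At stake is whether a significant slope can be mistaken for support of the conceptual model.

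**Working it through.** **Inputs from the documents.** Three randomised arms, 88 per arm, final sample 264 (Synopsis, Planned Sample Size; 3 × 88 = 264). Significance level 0.05 (Synopsis, Statistical Methods; two-sided assumed). The plan gives no figure for the regressions themselves, so there is none to reproduce.

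**Assumptions, because the documents give no effect sizes or SDs.** Changes in pain and in fear each have within-arm SD 1. They are uncorrelated within arms, so any link found is false. Both improve by 0 (no TENS), d/2 (placebo) and d (active).

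**Pooled slope without arm.** The arm means are 0, d/2 and d, with overall mean d/2. The between-arm variance of each change, and their between-arm covariance, is B = [(d/2)² + 0 + (d/2)²]/3 = d²/6. The slope, which here equals the correlation r, is B/(1 + B). The true within-arm slope is 0.

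**Approximate false-link rate.** The expected t is about r√262/√(1 − r²), with √262 = 16.19, compared with 1.96.

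- d = 0.5: B = 0.042, r = 0.04, t ≈ 0.65. Upper tail beyond 1.31 is 0.095, plus about 0.005 in the lower tail: 10%.
- d = 0.8: B = 0.107, r = 0.10, t ≈ 1.57. Tail beyond 0.39: 35%.
- d = 1.0: B = 0.167, r = 0.14, t ≈ 2.34. Tail beyond −0.38: 65%.

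**Simulation, 10,000 trials per setting, placebo at half the active effect:**

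| d | Pooled slope | False link, no arm term | False link, arm in model |
|---|---|---|---|
| 0.5 | 0.04 | 10.2% | 5.2% |
| 0.8 | 0.10 | 35.1% | 5.0% |
| 1.0 | 0.14 | 65.5% | 4.5% |

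**If only active TENS has an effect** (arm means 0, 0, d), B = 2d²/9:

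| d | Pooled slope | False link, no arm term | False link, arm in model |
|---|---|---|---|
| 0.3 | 0.02 | 6.2% | 4.9% |
| 0.5 | 0.05 | 14.1% | 4.9% |
| 0.8 | 0.12 | 52.4% | 4.9% |
| 1.0 | 0.18 | 85.0% | 5.2% |

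**Limit of the arm term.** Now suppose TENS does nothing, but a shared cause (for example, common self-report error) gives a within-arm correlation. In 4,000 trials per setting, a link is found in 90.8% without arm and 90.6% with arm at correlation 0.2, and in 99.9% either way at 0.3. Arm adjustment removes the between-arm part only.

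Baseline values were not part of these simulations.

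**The case against.** A reader might infer three things that go further than the documents allow.

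- **That the plan pools the arms and leaves treatment out by choice.** It does not say so. It names one predictor and is silent on arm and analysis set. Pooling is the plain reading of the text, but not the only one.
- **That Aim #2 makes no use of the randomisation.** It does. The group comparison by the Aim #1 model is a valid test of the effect of TENS on fear, fatigue, function and quality of life. The regressions are labelled as additional to it.
- **That an arm term would turn the regressions into a test of the pathway.** It would not, because pain change is not randomised; the shared-cause result shows this.

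The plan also already calls the results associations, and nothing in it says that a positive slope will be read as causal. The effect sizes, the half-size placebo effect and the zero within-arm correlation are all assumed. The pooled correlations of 0.04, 0.10 and 0.14 correspond to only about 0.2%, 1% and 2% of variance (r squared), and the 66% requires a full 1 SD effect on both measures.

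All of this stands and limits the point to the regressions. It does not remove it. The randomised comparison contains no pain term, so these regressions are all that Aim #2 offers on the link with pain. As written, they leave in a between-arm contribution that data already collected could take out.

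**Conclusion.** The point holds for the additional regressions and is a low-priority improvement. As specified, with change in pain as the only named predictor, a fit across the arms mixes between-arm and within-arm association. It can therefore report a link when TENS or expectation moves pain and the outcome separately.

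With 88 per arm, a two-sided 5% test, no within-arm link and placebo at half the active effect, the false-link rate is about 10%, 35% and 66% at d = 0.5, 0.8 and 1.0 SD, against about 5% with arm in the model. If only active TENS has an effect, the rates at those values are 14%, 52% and 85%. The bias is small at modest effects, and the documents do not say which effects to expect. The randomised Aim #2 comparison stands as planned.

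**What to change.** First reconcile the fear-change window between the Synopsis and the Data Analysis Plan table, since the TSK is scheduled only from visit 2. Then, for each Aim #2 regression:

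1. State the analysis set.
2. Add randomised arm and the V2 values of pain and of the outcome.
3. Report the arm-adjusted slope for pain change, and the arm effect with and without pain change.
4. Keep describing the slope as an association, and note that arm adjustment does not remove causes shared within arms. The same limit applies to comparing the arm effect with and without pain change.

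If a statement about the pathway itself is wanted, pre-specify an indirect-effect estimate together with its assumptions.

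The cost is a few model terms and sentences, and no new data. Some precision is lost if the arms differ in pain change. In the graded pattern above, if arm has no separate effect on the outcome, the standard error of the slope grows by a factor of about √(1 + d²/6): √1.042 = 1.02 at d = 0.5 and √1.167 = 1.08 at d = 1.0.

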Aim #3: To determine if active TENS alters pain processing in women with fibromyalgia and if improvement in clinical symptoms correlates with normalization of pain processing physiology. We will evaluate change in these physiologic parameters in responders versus non-responders as assessed clinically.

Aim #4: To determine if PROMIS is a useful instrument for assessing outcome for fibromyalgia by comparing to the revised version of the fibromyalgia impact questionnaire (FIQ-R).

Healthy Control Aims:

Aims:

Physically active women with fibromyalgia will have a similar phenotype (pain thresholds and conditioned pain modulation) and cytokine profile to physical active women without pain; conversely sedentary women with fibromyalgia will have a similar phenotype and cytokine release profile to sedentary women without pain.

Aim #5 will perform quantitative sensory testing to profile excitability and central inhibition in individuals with fibromyalgia and healthy controls; both sedentary and physically active individuals will be recruited in each cohort.

Aim #6 will examine for cytokine release profiles in immune cells (monocytes) from the sedentary and physically active individuals with and without fibromyalgia.

Study Synopsis

Protocol Title	Fibromyalgia Activity Study with TENS (Transcutaneous Electrical Nerve Stimulation)
Protocol Number	
Name of Sponsor	Funded by NIH NIAMS Performed at University of Iowa, Vanderbilt University
Investigational Product	TENS (Transcutaneous Electrical Nerve Stimulation) TENS is a non-pharmacological agent which delivers electrical stimulation by a battery operated device via electrodes placed on the skin. TENS is considered to be a safe, inexpensive and non-invasive modality used to treat a variety of acute and chronic pain conditions.
Phase of Development	Phase II Clinical Trial
Purpose of Study	The primary aim of the study is to test the effect of the long-term use of TENS on movement-related pain as measured by a numeric rating scale (NRS) during six minute walk test (6MWT) in women with fibromyalgia with random assignment to three treatments: standard care (No TENS), placebo TENS and active TENS.
Indication	Women with Fibromyalgia, ages 18-70
Number of Centers	The study will be conducted at 2 study sites: University of Iowa and the Vanderbilt University
Study Duration	5 years

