Exclusion Criteria	
 • Current or history of cardiovascular, pulmonary, neurological, endocrine, or renal disease that would preclude the involvement in the study. • TENS use in the last 5 years • Pacemaker • Uncontrolled blood pressure or diabetes • Neuropathic pain condition • Systemic autoimmune disorder (Lupus, PMR, RA, Psoriatic arthritis) • Spinal fusion – cervical or lumbar • Metal implants in the spine • Severe skin allergy to adhesive • Allergy to nickel • Pain less than 4 • Pregnancy • Epilepsy • Change in or new drug or treatment program within the last month or in the next 2months, i.e. must have a stable treatment plan • Unstable medical or psychiatric condition which in the opinion of the investigator could compromise the subject’s welfare or confound the study results
Planned Sample Size	Final sample size of 264 subjects divided into 88 subjects per group. We will recruit 316 subjects based on a 20% projected attrition.
Randomization	Patients will be randomly allocated on the second visit after a re-assessment of eligibility. We will use a permuted block schedule, stratified by site. The randomization schedule will be implemented using SAS v9.2 PROC PLAN, creating blocks of size 6 for each of the strata factors.
Study Device Dosage and Administration	
FDA Summary of Empi Select TENS Unit: TENS is a non-pharmacological agent which delivers electrical stimulation by a battery operated device via electrodes placed on the skin. TENS is considered to be a safe, inexpensive and non-invasive modality used to treat a variety of acute and chronic pain conditions.
 
510(k) Summary for 300 PV Complete Electrotherapy Systems 1. Manufacturer Empi [name]

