	
Contact Person: [name] [contact] Date Prepared: April 2, 2002
 
2. Device Name Proprietary Name: 300 PV Complete Electrotherapy System Common/Usual Name: Electrical Muscle and Nerve Stimulator Classification Names: Powered Muscle Stimulator, Transcutaneous Nerve Stimulator, interferential Current Stimulator, External Neuromuscular Functional Stimulator
 
3. TENS Parameters: Active and Placebo Units
 
 • TENS Frequency – 10 to 100 Hz, SMP mode • TENS Pulse Width - 200 µs • TENS Intensity - Maximal tolerable intensity • Duration: 2 h per day during activity. The 2 h may be broken into smaller segments of time with a minimum of 30 minutes. • Administration - Daily • TENS Location: TENS electrode on the skin will be a 4 x 7 butterfly electrode to the cervical and lumbar region. • Placebo TENS Unit - The placebo TENS unit will deliver current for 45s ramping to 0 in the last 15s.

Study Summary
	
This is a phase II randomized, double-blind, placebo controlled multi-center clinical trial involving a device, TENS, to assess the efficacy of TENS on pain with movement over a 1 month period in subjects with fibromyalgia. After participating in the 1 month random assignment, all subjects will receive active TENS for 1 month. Subjects will receive a phone call weekly from the study coordinator regarding progress.
 
 • Screening: Telephone screen for eligibility for the study • Assessor – performs baseline and all testing except TENS allocation and TENS home instruction. The assessor is blinded to TENS treatment. • TENS Allocator – performs TENS allocation, home instructions and questions regarding TENS

Demographic and Outcome Measures
	
 • Consent • Health History/Demographic • Vital Signs • Confirmation of ACR 1990 Criteria for FM/Tender Point Exam • 2010 ACR Criteria • NRS Rest Pain, Rest Fatigue, Movement Pain, Movement Fatigue • BPI • PROMIS • FIQR • SF-36 • MAF • TSK • IPAQ • PSQI • PSEQ • PCS

	
 • Global Impression of Change • Accelerometry (Actigraph) • 6MWT • STS • FR • PPT • CPM • TENS

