Criteria for Evaluation	
Primary Efficacy Endpoint:
 
 • Pain with movement (NRS) during 6MWT 
Secondary Efficacy Endpoints:
 
 • Health History/Demographics • Vital Signs • Confirmation of ACR 1990 Criteria for FM/Tender Point Exam • 2010 ACR Criteria • NRS Rest Pain, Rest Fatigue, Movement Pain, Movement Fatigue • BPI • PROMIS • FIQR • SF-36 • MAF • TSK • IPAQ • PSQI • PSEQ • PCS • Global Impression of Change • Accelerometry • 6MWT • STS • FR • PPT • CPM • TENS • Blinding
Statistical Methods	
 • Continuous variables will be summarized with descriptive statistics (n, mean, standard deviation, standard error, median, first and third quartiles, and minimum and maximum). • Categorical variables will be described with counts and percentages. The endpoints (VAS, BPI, PPT, CPM, and 6MWT, STS, FR and accelerometry measures) will be treated as continuous variables as well as scores from questionnaires (FIQR, SF-36, MAF, and TSK, PROMIS). • Changes from initial measurement to one month after randomization will be calculated for each of these endpoints. Changes in outcomes and percent changes in outcomes will be treated as continuous variables and will be summarized with descriptive statistics. Outcomes will be summarized by visit, as change from initial measurement, and percent

	
change from initial measurement. Continuous endpoints may also be categorized into discrete variables when appropriate. Shift tables may be utilized to investigate shifts in outcome categories from baseline to one month after randomization. SAS v9.2 or higher will be used for all analyses and a significance level of 0.05 will be used for all statistical tests. In the case that endpoints are found to be non-normal, appropriate transformations will be employed and non-parametric tests may be used

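### Whether active TENS alters pain processing (first part of Aim #3) has no randomised comparison: PPT and CPM are analysed only in active-TENS completers, by responder status

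*Combined protocol and SAP*

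**What the plan says.** The first part of Aim #3 is a question about a treatment effect: "To determine if active TENS alters pain processing in women with fibromyalgia". The second part asks whether clinical improvement goes with normalised physiology, to be examined in responders against non-responders.

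The synopsis (Statistical Methods, Aim #3) sets the primary endpoints as visit 3 minus visit 2 change "in PPT and DNIC/CPM for those who complete one month of active TENS". It compares responders with non-responders by the Aim #1 method and acknowledges that responder status is not randomised. The Aim #3 row of the Data Analysis Plan repeats the restriction to active-TENS completers. It lists only responder classification and a regression on predictors.

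The Aim #1 method is a mixed model with group, time and their interaction: "The test for the treatment group*time interaction effect corresponds to the test comparing mean change among the groups". The planned size is stated as "Final sample size of 264 subjects divided into 88 subjects per group".

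**The concern.** Women assigned to placebo or standard care start active TENS only after the randomised month. A visit 3 minus visit 2 change after a month of active TENS therefore exists only in the active arm. The specified analysis removes both control groups and then splits the remaining arm by an outcome observed after randomisation.

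Three consequences follow for the first part of the aim.

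- An effect shared by all active subjects cancels out of the responder contrast, whatever its size.
- The contrast can be significant when TENS does nothing, because women whose pain falls for any reason may also show higher thresholds.
- The time effect in the same model would register a shared shift, but it cannot separate TENS from placebo response, repeat testing or regression to the mean.

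Restoring central inhibition is part of the trial's stated hypothesis. The preliminary result in the Study Rationale is itself placebo-controlled: PPT during DNIC rose 20% with active TENS against 1% with placebo. As written, the larger trial specifies no such comparison. Restricting to completers also departs from the intention-to-treat approach used for Aim #1.

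**Working it through.** **1. Is the comparison specified elsewhere?** The plan gives no sample size or power figure for Aim #3, so there is nothing to reproduce. These are the other places that could supply a randomised comparison:

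| Place | Content | Closes the gap? |
|---|---|---|
| Aim #1, synopsis and Data Analysis Plan | Movement pain across the three arms | No: PPT and CPM not named |
| Aim #1, synopsis, adjusted analysis | "a secondary comparison of the change in endpoints for the three groups will be made by expanding the linear mixed model" | No: applies only if adjustment is needed, and sits under Aim #1 |
| Aim #2, both places | Fear of movement, function, fatigue, resting pain, rescue medication, quality of life | No: PPT and CPM absent |
| Synopsis, Criteria for Evaluation | PPT and CPM listed as secondary efficacy endpoints, beside demographics, vital signs and blinding | No: no contrast given |
| Synopsis, Statistical Methods (general) | "Changes in outcomes and percent changes in outcomes will be treated as continuous variables and will be summarized with descriptive statistics"; also "a significance level of 0.05 will be used for all statistical tests" | No: testing seems intended, but the groups are not named |
| Data Analysis Plan, General Considerations | Descriptive summaries, with a non-parametric fallback | No: groups not named |
| Data Analysis Plan, Exploratory Analysis | Sensory change related to pain and quality-of-life change | No: not compared by arm |

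**2. What the responder contrast shows when TENS has no effect.** From the plan: 88 active subjects and a 0.05 level (two-sided assumed). Further assumptions: pain change and PPT change are bivariate normal with correlation r; responders are the best fraction p on pain change; two-sample t-test without covariates; 20,000 simulated trials. With p = 0.3 the groups are 26 and 62. Percentage of trials significant:

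| r | 0 | 0.1 | 0.2 | 0.3 | 0.5 |
|---|---|---|---|---|---|
| p = 0.3, no shift | 5 | 11 | 29 | 57 | 97 |
| p = 0.3, 0.5 SD added to all 88 | 5 | 11 | 29 | 57 | 97 |

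At r = 0.3 the figure is 51% with p = 0.2 and 62% with p = 0.5. For the correlation question these rates are genuine power. They are errors only if read as evidence of a TENS effect.

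**3. The time effect within active subjects** (average of the two subgroup means, r = 0). SE = 0.5 × √(1/26 + 1/62) = 0.117 SD of change. A shared 0.5 SD shift gives 0.5/0.117 ≈ 4.28 and is detected in 99% of trials (noncentral t, 86 df). A purely non-specific shift is also flagged: 39% of trials at 0.2 SD and 72% at 0.3 SD. Active versus placebo stays at 5% when both arms share the shift.

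**4. The randomised contrast, 88 versus 88.** SE = √(2/88) = 0.151 SD, so 0.5 SD gives 0.5/0.151 ≈ 3.32 (noncentral t, 174 df).

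| Level | Power for 0.5 SD | Detectable at 80% power |
|---|---|---|
| 0.05 | 91% | 0.42 SD |
| 0.05/3 | 81% | 0.49 SD |
| 0.05/6 | 74% | 0.53 SD |

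**5. Which reading?** The Order of Testing table lists PPT before and after TENS starts in Session 2. In Session 3 it lists PPT before and during TENS Treatment 1, and again under Treatment 2 after debriefing. Before Treatment 2 that allows 2 × 2 = 4 visit 3 minus visit 2 changes per site, or 4 × 3 = 12 over the three PPT sites in Table 3 (List of equipment).

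CPM in Session 2 appears only after TENS starts. This reading is of low confidence because the table was flattened in extraction. If it is right, the visit 2 CPM value is not an untreated baseline in the active arm, while the control arms differ: "The placebo TENS unit will deliver current for 45s ramping to 0 in the last 15s", and standard care has no TENS.

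**6. Model type.** The Data Analysis Plan uses linear regression for predictors of responder status, a binary outcome. The synopsis uses logistic regression.

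**The case against.** The strongest reply is that Aim #3 states its own evaluation, responders against non-responders, and the synopsis carries it out. On that view only one clause of a non-primary aim is affected, and Aim #1 is untouched. This stands as a limit on reach. It does not answer the first clause, which asks about an effect of treatment.

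A second reply is that a comparison of arms is probably intended, since PPT and CPM are secondary efficacy endpoints of a placebo-controlled trial and the adjusted-analysis sentence speaks of endpoints in the plural. That is plausible. But the sentence is conditional and sits under Aim #1, and the only population written for these endpoints excludes the controls.

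A third reply is that the rates rest on assumptions. This is fair: the published responder criteria are not reproduced in the plan, and the covariates expected in the responder model are left out of the simulation. Covariates could change the rates, but they would not make the contrast randomised. That a shared shift cancels is algebra and needs no assumption about size.

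Finally, the choice of reading and the linear/logistic mismatch are separable, and the CPM timing point is uncertain. They are kept as secondary points because a visit 3 minus visit 2 comparison cannot be run until its readings are named.

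**Conclusion.** The concern holds. Followed as written, the plan gives no controlled answer to the first part of Aim #3, and the analysis it does specify cannot supply one. Confidence in this is high because it rests on the text alone.

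The size is illustrative. At an assumed 30% responder rate, the responder contrast is significant in 11% to 97% of trials with no TENS effect for correlations of 0.1 to 0.5, and it does not respond to a shared shift. The randomised contrast has 81% to 91% power for an assumed 0.5 SD effect, depending on the level, if all 88 per arm are analysed.

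The plan should be changed on this point. The primary aim and the responder question are not affected.

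**What to change.** For the first part of Aim #3, specify a three-arm comparison in all randomised subjects.

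- **PPT:** use the Aim #1 group-by-time model with the visit 2 pre-TENS reading as baseline. Name one visit 3 reading taken before open-label Treatment 2: pre-TENS for a lasting effect, or during Treatment 1 for an effect under stimulation. Name one site or a summary over sites.
- **CPM:** compare arms at the visit 3 reading taken during Treatment 1. Check the source order-of-testing table first. If the visit 2 reading precedes TENS, use the same model as for PPT; if it follows the start of TENS, do not treat it as an untreated baseline.
- **Multiplicity:** apply the Aim #1 Bonferroni adjustment for three pairwise contrasts within each of PPT and CPM.
- **Responders:** keep that comparison as a secondary association for the second part of the aim, and use logistic regression for responder status in the Data Analysis Plan as in the synopsis.

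The cost is SAP wording and a few models. PPT and CPM are already scheduled at visits 2 and 3 without restriction by arm, so no patients, visits or procedures are added. The adjustment lowers power for 0.5 SD from 91% to 81%, or to 74% if alpha were also split over the two measures, which the plan does not require. The CPM comparison may lose its change-score form.
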